### Survival analysis

Five proportional hazards model will also be run to look at early drop-out, with and without the disease progression measures above (including by *any* measure). Kaplan-Meier curves will be used to illustrate time to drop-out for the different treatments.

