# Secondary Endpoints

The secondary endpoints involve measures of disease progression from baseline to 12 months, assessed by serial multi-parametric magnetic resonance imaging (MRI) of the prostate, serum PSA measurement, and prostate biopsy.

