## Biochemical disease progression

Biochemical disease progression (or regression) will be defined as a 50% increase (or decrease) in serum PSA at 12 months from baseline.

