## Study period and visits

The study will last for 18 months (plus ≥30 days for pharmacovigilance). Data will be collected at 3-monthly intervals. Secondary endpoint measures will be carried out at the following times:

- MRI taken at baseline and 12 months
- Prostate biopsy at baseline and 12 months for pathology review & CCP score analysis.
- Serum PSA measured at baseline and every 3 months until 18 months
- Serum testosterone, FSH, and LH at baseline and every 6 months until 18 months
- Serum vitamin D3 taken at baseline and every 6 months until 18 months
- Serum calcium at screening and 6, 12, and 18 months

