#### 5. Disease **progression** by any measure

A final logistic regression model will be run to assess the effect of treatment on disease progression by any of the three measures (tumour volume, serum PSA, Gleason score). Disease progression will be coded as 1 if disease progression is observed for any of the three disease measures and 0 otherwise. A regression of disease — a decrease in disease measure — will be treated as "no progression".

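### Drop-out models that include month-12 progression: the any-measure model can make progression look falsely protective, and the other four lose every drop-out before month 12

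*SAP*

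**What the plan says.** The Survival analysis section of the SAP plans: "Five proportional hazards model will also be run to look at early drop-out, with and without the disease progression measures above (including by *any* measure"). It adds that "Kaplan-Meier curves will be used to illustrate time to drop-out for the different treatments". It does not say how progression enters the model, what the time origin is, what counts as drop-out, or what happens to a man with no progression result.

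The five models match the five progression outcomes defined just before: tumour volume, PSA, Gleason, maximum cancer core length and any measure. All are month-12 results:

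- Secondary Endpoints describes "measures of disease progression from baseline to 12 months".
- Study period and visits lists "MRI taken at baseline and 12 months" and "Prostate biopsy at baseline and 12 months".
- PSA is sampled every 3 months to month 18, but Biochemical disease progression defines the event as a "50% increase (or decrease) in serum PSA at 12 months from baseline".

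For the composite, the section on progression by any measure says: "Disease progression will be coded as 1 if disease progression is observed for any of the three disease measures and 0 otherwise". The three-level codings of the other four outcomes have no level for a man who was not assessed.

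**The concern.** On the natural reading, progression is a covariate in a model for time from randomisation to drop-out over 18 months. A man who leaves the study at month 4 never has a month-12 result, so the covariate is missing for the very men whose early drop-out is being modelled. The SAP's codings then lead to two different problems.

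1. **Any-measure model.** He is coded 0. All drop-outs before month 12 fall among the non-progressors, and the men coded 1 are by construction those who stayed at least 12 months. Progression can appear to protect against drop-out even if it has no effect or raises the risk.
2. **The other four models.** He has no code and is excluded. The model with progression then covers drop-out in months 12-18 only, while the model without it covers months 0-18. A change in the treatment effect between the two could be read as progression explaining drop-out, when only the men and the period have changed.

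Drop-out by arm is useful for planning the 800-patient trial, so a reversed or mismatched hazard ratio could mislead that planning.

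**Working it through.** **Inputs.** From the SAP: 18 months of follow-up, progression determined at month 12, 102 men. The SAP gives no drop-out or progression rate, so there is no figure of its own to reproduce. Assumed: 30% progression; 5% drop-out in months 12-18 among men still in the study; 5%, 10% or 20% drop-out before month 12, unrelated to progression; constant hazard within each period.

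**Share of drop-outs before month 12, if progression has no effect.** With early risk e, the share is e / [e + (1 − e) × 0.05]:

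- e = 5%: 0.05 / (0.05 + 0.0475) = 51%
- e = 10%: 0.10 / (0.10 + 0.045) = 69%
- e = 20%: 0.20 / (0.20 + 0.04) = 83%

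**Any-measure model, early leavers coded 0.** Simulated Cox models from month 0 gave:

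| Drop-out before month 12 | Progression HR, truth 1 | Progression HR, truth 2 (after month 12) |
|---|---|---|
| 5% | 0.39 | 0.84 |
| 10% | 0.25 | 0.47 |
| 20% | 0.14 | 0.28 |

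A month-12 landmark model recovers about 1 and about 2.

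**Check of the middle row by hand (truth 1).** The Cox estimate θ makes the observed number of drop-outs among men coded 1 equal to the number expected from the risk sets.

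- Drop-outs among men coded 1, per man randomised: 0.90 × 0.05 × 0.30 = 0.0135, all after month 12.
- Men coded 1 as a share of the risk set: 0.30 × 0.90 = 0.27 at month 0, rising to 0.30 at month 12; average about 0.285.
- Equation: 0.0135 = 0.10 × 0.285θ / (0.715 + 0.285θ) + 0.045 × 0.30θ / (0.70 + 0.30θ).
- At θ = 0.25 the right side is 0.10 × 0.0906 + 0.045 × 0.0968 = 0.0091 + 0.0044 = 0.0134. So θ is about 0.25, as simulated.

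The same equation, integrated over time, gives 0.41, 0.25 and 0.14 for truth 1, and 0.80, 0.49 and 0.27 for truth 2. The small differences from the table are simulation error.

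**Other four models, unassessed men excluded.** No remaining man drops out before month 12, so the Cox model from month 0 and the month-12 landmark model have the same risk sets at every drop-out. In one run (n = 8,000, 10% early drop-out) both gave 1.0518 with truth 1, and both gave 1.7447 with truth 2. There is no false protection here. What changes is the treatment effect: if aspirin doubled drop-out before month 12 only (10% on placebo), the treatment HR would be 1.69 in all men and 1.01 in the men kept in the model with progression.

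**At the size of this trial.** Expected drop-outs after month 12 are 102 × (1 − e) × 0.05, that is 4.8, 4.6 and 4.1 for e = 5%, 10% and 20%. In a separate simulation with n = 102, a constant hazard throughout and no true effect, the any-measure coding gave a median HR of 0.21 to 0.27. False protection was significant in 1-9% of trials at 10% total drop-out, 3-60% at 20% and 18-89% at 30%; the lower figure is for 20% progression and the upper for 40%. These figures are indicative, since some small-sample fits did not converge.

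**The case against.** **The section does not say covariate, fixed, or from month 0.** This is true. It could mean counting progression as part of the event, and it does not rule out a time-dependent covariate. Adding measures to a hazards model most naturally means adding covariates, however, and text that leaves both role and timing open needs settling anyway.

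**Drop-out is not defined.** If it means stopping treatment, a man who stops at month 4 might still have the month-12 MRI and biopsy, and fewer men would be lost. A month-12 value would still be used to explain an earlier event.

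**Exclusion causes no immortal-time bias.** This stands. A reader might infer that all five models make progression look protective, because men who reach month 12 carry guaranteed event-free time. In a Cox model, time before the first drop-out in the analysed set contributes nothing to the hazard ratio. The false protection therefore belongs to the any-measure model alone, and only if its logistic coding is carried over. Excluding unassessed men there would remove it. A landmark model would lose the same early drop-outs.

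**Early drop-out is still analysed.** This also stands. The Kaplan-Meier curves and the models without progression retain every man.

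**The analysis is minor.** The main objective and primary endpoint concern recruitment, and drop-out is not a listed secondary endpoint. At 10% total drop-out, a falsely significant result would be uncommon. This limits the weight of the point but does not make the estimate correct.

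**Conclusion.** The point holds, with a limited scope. In the any-measure model, the stated coding applied to drop-out puts all men who leave before month 12 among the non-progressors and pulls the progression hazard ratio far below its true value. The direction is reversed when progression in fact doubles later drop-out. In the other four models the progression hazard ratio is free of that artefact, but the model holds only drop-outs from months 12-18, so its treatment effect must not be set beside that of the model without progression.

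The document does not support the wider reading that every model is biased or that early drop-out vanishes from the analysis. The sizes rest on assumed rates and on reading progression as a fixed covariate from randomisation, with drop-out meaning leaving the study. This should be corrected before analysis. The primary endpoint and the treatment-only drop-out models are not affected.

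**What to change.** Amend the Survival analysis section as follows.

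- State the time origin (randomisation) and define drop-out.
- Keep the Kaplan-Meier curves and the treatment-only hazards models in all men from randomisation.
- Enter progression as a time-dependent covariate, equal to 0 for everyone until the date of the month-12 assessment and taking the observed result from then on. Before that date no contrast on progression exists, so early leavers inform the treatment effect without counting as non-progressors.
- Do not carry the zero-otherwise coding over to men who left before assessment. State a rule for men still followed after month 12 without a result, for example censoring at the scheduled assessment in that measure's model, with the number reported.
- A month-12 landmark model is an acceptable alternative for the progression hazard ratio only. Its treatment effect should not be compared with that of the all-men model.

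This costs a few sentences and needs no new data. The progression hazard ratio will rest only on drop-outs in months 12-18, about 4 to 5 men under the assumptions above, so label it descriptive and expect wide intervals.

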## Supplementary analyses

## Change in disease progression measures

The effect of treatment on the non-dichotomised change in disease measures will be explored. The differences in tumour volume, serum PSA and maximum cancer core length from baseline to 12 months will each be treated as the dependent variable. Serum PSA will be transformed to log (1+PSA). Patients without a second MRI or biopsy will be excluded from specific analyses where change was based on that measure.

Linear regression will be used to assess the effect of each treatment on disease progression, both univariate (treatment Y/N), and adjusted for the other treatment. Further analyses will adjust for serum hormone levels (testosterone, FSH, LH), and include an interaction term between aspirin and vitamin D3.

A Wilcoxon rank sum test will be performed to look at treatment differences using the change from baseline for each disease measure. For aspirin, the 100mg and 300mg doses will be combined for comparison to the placebo and also compared separately. All tests will be stratified by the other treatment and un-stratified. A Wilcoxon test for trend (Cuzick test) will also be carried out to determine whether there is an increased change in disease measure with increased aspirin dose.

Further exploratory analyses to look at time to change may be undertaken using a mixed effects model applied to log (1+PSA). As before, aspirin and vitamin D3 will be included as predictors, with an interaction effect and covariates included. Covariates may include age, BMI, or hormone levels. The interaction term will be removed if not significant. A plot of log (1 + PSA) will be generated, containing the predicted trajectories by treatment arm.

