## Disease progression by MRI

Disease progression by MRI of the prostate will be defined as an increase in lesion volume of  $\geq$ 33% or an upgrading of MRI stage of disease to  $\geq$ T3. Disease regression by MRI will be defined as a decrease in lesion volume of  $\geq$ 33% or the absence of a lesion at 12 months where one was detected at baseline. In the case where no lesion was identified by MRI screening, disease progression will be defined as the development of a lesion of 0.2cc or greater and being assigned a PIRADS score of 4 or 5.

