### Change in serum hormone levels and CCP score

The effect of treatment on testosterone, FSH, LH, and CCP will be investigated using an ANOVA model. The difference in serum hormone concentration from baseline to 18 months for each of the hormones, or the difference in CCP score from baseline to 12 months will act as the dependent variable. Treatment will be the independent variable, and a treatment interaction term may also be added. The hormone concentrations will be log-transformed, as with PSA.

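### The supplementary models of change from baseline omit the baseline value of the measure analysed, and so give up precision that data already collected could supply

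*SAP*

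**What the plan says.** Two parts of the SAP's supplementary analyses model a change score.

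- **Change in disease progression measures.** The outcomes are defined thus: "The differences in tumour volume, serum PSA and maximum cancer core length from baseline to 12 months will each be treated as the dependent variable". PSA is analysed as log(1+PSA), and men without a second MRI or biopsy drop out of the analyses that need it. The linear regressions are "both univariate (treatment Y/N), and adjusted for the other treatment". Then: "Further analyses will adjust for serum hormone levels (testosterone, FSH, LH), and include an interaction term between aspirin and vitamin D3".
- **Change in serum hormone levels and CCP score.** The ANOVA outcomes are "The difference in serum hormone concentration from baseline to 18 months for each of the hormones" (log-transformed), or "the difference in CCP score from baseline to 12 months will act as the dependent variable". The model terms are: "Treatment will be the independent variable, and a treatment interaction term may also be added".

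The baseline values are collected. The list in Study period and visits has MRI, biopsy and PSA at baseline, and for the hormones: "Serum testosterone, FSH, and LH at baseline and every 6 months until 18 months".

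The SAP does adjust for baseline in two other models: the logistic model of hormones and CCP on progression, and the regression of 12-month PSA on serum vitamin D3. Those statements apply only to their own models, and no general rule extends them.

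**The concern.** The SAP lists the terms of each change model, and the outcome's own baseline is not among them. Adjusting for testosterone, FSH and LH does not stand in for baseline tumour volume, PSA or core length. An analyst following the text would leave baseline out.

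A change score subtracts the whole baseline value, as if the slope of follow-up on baseline were 1. When the slope is below 1, as with regression to the mean, the subtraction over-corrects. A group that starts high by chance then tends to show too large a fall. Averaged over randomisations this is not bias; it is extra variance. Including baseline lets the data estimate the slope and removes that component.

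At stake are the standard errors of the continuous-scale treatment effects, in a trial with at most 102 men and fewer for MRI and biopsy. Apart from an optional mixed model for PSA, these are the SAP's only regression estimates of treatment effect on continuous outcomes.

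The point does not reach the Wilcoxon tests, the optional PSA mixed model (which may carry baseline PSA as a repeated outcome) or the ordinal and logistic progression models.

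**Working it through.** **Nothing to reproduce.** The SAP gives no SD, correlation or power for these models. Its one power figure concerns recruitment and has no bearing here.

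**Inputs.** N = 102 (SAP, Sample size). Equal allocation to six groups gives 102/6 = 17 each. Vitamin D3 is then 3 × 17 = 51 v 51, and aspirin is 2 × 17 = 34 placebo v 4 × 17 = 68 active. Assumed: all 102 analysed, a linear relation between baseline and follow-up, and r from 0.3 to 0.9.

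**Step 1: variance, equal SD s at both times.**

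- Change without baseline: 2s²(1−r).
- Change with baseline as covariate: s²(1−r²).
- Ratio: (1−r²)/[2(1−r)] = (1+r)/2.

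**Step 2: detectable difference** (two-sided 5%, 80% power, in units of s).

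- Multiplier: 1.9600 + 0.8416 = 2.8016.
- Design factor: √(2/51) = 0.198 for vitamin D3; √(1/34 + 1/68) = 0.210 for aspirin.
- Detectable difference: 2.8016 × design factor × √[2(1−r)] without baseline, or × √(1−r²) with it.

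| r | Variance ratio | SE ratio | Vitamin D3, without → with baseline | Aspirin, without → with baseline |
|---|---|---|---|---|
| 0.3 | 0.65 | 0.81 | 0.656 → 0.529 | 0.696 → 0.561 |
| 0.5 | 0.75 | 0.87 | 0.555 → 0.480 | 0.588 → 0.510 |
| 0.7 | 0.85 | 0.92 | 0.430 → 0.396 | 0.456 → 0.420 |
| 0.9 | 0.95 | 0.97 | 0.248 → 0.242 | 0.263 → 0.256 |

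At r = 0.5 the variance ratio of 0.75 is worth 1/0.75 = 1.33 times as many men.

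**Step 3: finite-sample check.** A simulation of the 3×2 design with 102 men (4000 runs for each r) compared the vitamin D3 estimates with and without baseline. The ratio of their standard errors was 0.871 at r = 0.5, 0.930 at r = 0.7 and 0.974 at r = 0.9. With a true effect of zero, every mean estimate lay within 0.003 of zero. The lost degree of freedom therefore costs almost nothing, and neither estimator is biased.

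**Step 4: unequal variances.** Let k be follow-up SD divided by baseline SD. The ratio becomes k²(1−r²)/(1+k²−2rk). The denominator equals k²(1−r²) + (1−rk)², so the ratio cannot exceed 1 and equals 1 only when rk = 1.

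- k = 0.8: 0.50, 0.57, 0.63 and 0.61 at r = 0.3, 0.5, 0.7 and 0.9. The peak is 0.64, at r = 0.8.
- k = 1.25: 0.78, 0.89, 0.98 and 0.95 at the same r. At r = 0.8 it is 1.00, so there is no gain.

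**Step 5: chance imbalance.** The randomisation blocks balance treatment numbers, and the SAP names no baseline factor. A one-standard-error baseline imbalance is 0.198 SD (51 v 51) or 0.210 SD (34 v 68). It shifts the change contrast by that amount times (1−r). At r = 0.5 this is 0.198 × 0.5 = 0.099 SD or 0.210 × 0.5 = 0.105 SD; at r = 0.9 it is about 0.02 SD. This is the mechanism behind Step 1 and not a second loss: 2(1−r) = (1−r²) + (1−r)², and the last term is the imbalance component.

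**The case against.** The strongest reply is that nothing here is invalid. An unadjusted change score is an unbiased estimator, the analyses are labelled supplementary, and the SAP sets no power target for them. The primary endpoint is recruitment, and the main treatment comparisons are the progression proportions and the ordinal and logistic models. All of that stands, and it limits the weight of the point.

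Four narrower objections also have force.

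- **The gain depends on an unknown r.** It is negligible near r = 0.9 and vanishes when rk = 1. The omission is certain; the size of the benefit is not.
- **The link to planning is loose.** The SAP already gives 800 men for the definitive trial and uses this trial mainly to set the number of centres. The Introduction does name potential numbers as part of the main objective, but no section says these coefficients feed that calculation. The SDs and correlations useful for planning can be computed whichever model is fitted.
- **PSA has another route.** The optional mixed model of log(1+PSA) also yields treatment coefficients. It covers PSA only and need not be run.
- **Tumour volume is a special case.** The MRI definitions provide for men with no lesion at screening and for "the absence of a lesion at 12 months where one was detected at baseline". How such men enter a linear model is unsettled with or without baseline adjustment, and linearity is least assured there.

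None of this supplies a reason for leaving baseline out. Apart from one degree of freedom, adjustment cannot lose precision in the linear setting of Step 4. It excludes nobody, because every man with a change score has a baseline value.

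**Conclusion.** The concern holds, as a loss of precision and not of validity. Under the equal-variance, linear assumptions, adjustment would cut the variance of the treatment estimates by 5% to 35% for r between 0.9 and 0.3. The standard error falls by about 13% at r = 0.5 and 2.5% at r = 0.9. If follow-up values are less variable than baseline the gain can be larger, up to half the variance at k = 0.8 and r = 0.3. If they are more variable it can shrink to nothing. These figures assume all 102 men are analysed; the loss of men without a second MRI or biopsy widens both sets of intervals. The improvement is worth making because it is almost free, but no primary or main secondary conclusion depends on it.

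**What to change.** In the section on change in disease progression measures, state that each linear model includes the baseline value of the measure analysed, on the same scale as the outcome (log(1+PSA) for PSA). In the section on change in hormones and CCP score, state the same for that model, with hormone baselines log-transformed as the outcomes are.

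For tumour volume, also say how men with no baseline lesion enter the model, for example through a no-lesion indicator, and that linearity in baseline volume will be checked.

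The present models without baseline can stay as sensitivity analyses.

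The cost is a change of SAP wording and one degree of freedom per model, or two for tumour volume if the indicator is used. No extra data are needed, since the baseline values are already required to compute the change.

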### Change in serum hormone levels and CCP score

The effect of treatment on testosterone, FSH, LH, and CCP will be investigated using an ANOVA model. The difference in serum hormone concentration from baseline to 18 months for each of the hormones, or the difference in CCP score from baseline to 12 months will act as the dependent variable. Treatment will be the independent variable, and a treatment interaction term may also be added. The hormone concentrations will be log-transformed, as with PSA.

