## Serum hormone levels

Levels of serum testosterone, Follicle Stimulating Hormone (FSH), and Luteinizing Hormone (LH) will be measured every 6 months. Analyses will focus on whether serum levels have an effect on disease progression, and whether the serum concentrations differ between treatment arms.

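### The hormone ANOVA uses only the unadjusted change to 18 months, so the 6- and 12-month samples do not enter it and men without an 18-month sample are excluded

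*SAP*

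**What the plan says.** The SAP section on study period and visits schedules "Serum testosterone, FSH, and LH at baseline and every 6 months until 18 months", which gives three post-baseline values per man. The section on serum hormone levels names as one of its two questions "whether the serum concentrations differ between treatment arms", without tying it to a visit.

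The analysis is in the section on change in serum hormone levels and CCP score: "The effect of treatment on testosterone, FSH, LH, and CCP will be investigated using an ANOVA model". For hormones the outcome is "The difference in serum hormone concentration from baseline to 18 months for each of the hormones", after a log transform. Treatment is the independent variable and an interaction between treatments is optional. The section names no visit term, no baseline covariate and no rule for a missing 18-month value. It follows under the heading "Supplementary analyses".

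Two other places bear on the point. The survival analysis section says "Five proportional hazards model will also be run to look at early drop-out", so men leaving early are expected, but no rate is given. The only mixed model in the SAP is an optional exploratory one for log(1+PSA).

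**The concern.** The SAP describes one test of treatment on hormones. Elsewhere, hormone levels serve as covariates or as predictors of progression, which does not answer whether treatment changes them.

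A change score to 18 months needs an 18-month value. A man who gave samples at 6 and 12 months and then left contributes nothing, and cumulative drop-out is greatest at the visit chosen. With about 102 men spread over a 3x2 design, losing men who have usable data is a needless cost. Subtracting baseline instead of adjusting for it costs further precision, because the change score carries the full noise of the baseline measurement.

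**Working it through.** The SAP gives no SD, correlation, drop-out rate, power or sample size for the hormone analysis, so there is no planned figure to reproduce. What follows is relative variance under stated assumptions.

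**Inputs.** From the SAP: 102 men; hormone samples at baseline, 6, 12 and 18 months. Assumed: equal SD at all visits, set to 1; correlation ρ either equal between all visits or falling with distance (AR(1)), with ρ from 0.5 to 0.9; drop-out of 10 or 20%, spread evenly over the three six-month intervals.

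**1. Complete data, equal correlation.** The variances, up to a common factor, are:
- 18-month change score: 2(1−ρ)
- 18-month value adjusted for baseline: 1−ρ²
- mean of the three post-baseline values, adjusted for baseline: (1+2ρ)/3−ρ²

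| ρ | change score | 18-month value, adjusted | ratio to change | mean of three, adjusted | ratio to change |
|---|---|---|---|---|---|
| 0.5 | 1.00 | 0.75 | 0.75 | 0.417 | 0.42 |
| 0.6 | 0.80 | 0.64 | 0.80 | 0.373 | 0.47 |
| 0.7 | 0.60 | 0.51 | 0.85 | 0.310 | 0.52 |
| 0.9 | 0.20 | 0.19 | 0.95 | 0.123 | 0.62 |

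The first ratio is (1−ρ²)/[2(1−ρ)] = (1+ρ)/2. Baseline adjustment therefore cuts the variance of the 18-month contrast by 15 to 25% at ρ of 0.5 to 0.7, and by 5% at 0.9. This needs no intermediate sample.

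**2. What the 6- and 12-month samples add to the 18-month contrast.** With complete data they add nothing (ratio 1.00). With drop-out d, the completers' change score has variance 2(1−ρ)/(1−d). At ρ = 0.5 and d = 0.2 that is 1.00/0.80 = 1.25. A likelihood-based repeated-measures analysis of the same 18-month change gives 1.169, a ratio of 0.935. Over both correlation patterns and ρ of 0.5 to 0.9:
- 10% drop-out: ratio 0.951 to 0.978, a cut of 2 to 5%
- 20% drop-out: ratio 0.900 to 0.954, a cut of 5 to 10%

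These compare change with change. If both analyses are already adjusted for baseline, the added gain under equal correlation is smaller: 1 to 2% at 10% drop-out (ratio 0.982 to 0.990) and 2 to 4% at 20% (0.962 to 0.980).

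**3. Both parts together.** Under equal correlation of 0.5 to 0.7, the baseline-adjusted repeated-measures estimate at 18 months, relative to the completers' change score, has ratio 0.743 to 0.838 at 10% drop-out and 0.735 to 0.825 at 20%. The cuts are 16.2 to 25.7% and 17.5 to 26.5%.

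**4. Men.** At 10% and 20% drop-out, 102 × 0.10 ≈ 10 and 102 × 0.20 ≈ 20 men leave the ANOVA, and the standard error rises by factors 1/√0.9 = 1.05 and 1/√0.8 = 1.12. With even spread, two thirds of them have at least one post-baseline sample: 10.2 × 2/3 ≈ 7 and 20.4 × 2/3 ≈ 14 men who could be kept.

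**5. A different target.** For the mean of the three changes under equal correlation, the variance is 4(1−ρ)/3. Divided by 2(1−ρ) this is 2/3 at any ρ, a cut of 33%. Under AR(1) of 0.5 to 0.9 the cut is 41 to 47%. Adjusting this mean for baseline as well gives the ratios of 0.42 to 0.52 in the last column of the table for ρ of 0.5 to 0.7.

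**The case against.** The best defence is that the 18-month target is a legitimate choice. It is the end of the study, adherence is assessed up to that visit, and it reflects the longest exposure. The untimed hormone question permits an average over visits but does not require one. An end-of-study comparison is neither an error nor a contradiction. This stands, and it is why the 18-month contrast should remain the main result.

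A reader might infer that leaving out two of three post-baseline samples throws away much of the available precision. The documents do not support that. Two thirds is a count of samples, not of information about the 18-month effect. The ratios of 0.42 to 0.52 arise only by moving to the average over visits and adding baseline adjustment. For the target that the SAP names, the intermediate samples matter only through drop-out, and then modestly.

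A reader might also infer an inconsistency with PSA. There is none to press. PSA is taken every 3 months and hormones every 6, the PSA mixed model is optional, and the planned continuous PSA analyses also use a single change, to 12 months.

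Nor can one say that the 6- and 12-month samples go unused throughout the SAP. Hormone levels are also covariates in other models, and the visit is not specified there. The point is confined to this ANOVA.

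What survives is narrower. Men with usable samples are excluded and baseline is used inefficiently, and both can be mended without giving up the 18-month target.

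**Conclusion.** The concern holds as an avoidable inefficiency in one supplementary analysis. For the 18-month contrast, baseline adjustment cuts variance by 15 to 25% at an assumed correlation of 0.5 to 0.7, and by less if the correlation is higher. Use of the intermediate samples is worth nothing with complete data and roughly 2 to 10% at an assumed 10 to 20% drop-out, measured change against change. The gain of about a third or more belongs only to the average over visits.

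All of these figures rest on assumed correlations, equal SDs and assumed drop-out, since the SAP supplies none of them. Keeping the early leavers also relies on their missing values being explained by the data that were observed. The primary endpoint is recruitment and no decision stated in the SAP turns on the hormone result, so the priority is low.

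**What to change.** For hormones only, replace the ANOVA with a repeated-measures model on the log values at 6, 12 and 18 months:
- fixed effects for log baseline, visit, aspirin, vitamin D3 and treatment-by-visit;
- correlation between a man's repeated values allowed for;
- the optional aspirin-by-vitamin D3 interaction kept;
- every man with at least one post-baseline value included.

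Name the 18-month contrast as the main result and give the average over visits as an additional summary. Leave the CCP analysis at 12 months as it is, because CCP has only one post-baseline measurement.

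The cost is a short change to the SAP and slightly more programming. No new data are needed.
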